### 10.3.2 ANALYSIS OF THE PRIMARY EFFICACY ENDPOINT(S)

The purpose of the qualitative data analysis, which will address the primary aim of this project, is an in-depth understanding of patients' perceived usefulness of the ACT intervention for promoting management of chronic pain. Analysis will begin with the transcription of each semi-structured interview into the coding software program. Qualitative analyses will be conducted using ATLAS.ti software, which will store, code, and categorize data transcripts. For this project data will be analyzed with a constant comparative approach [24]. This is an inductive approach to data analysis through which each piece of data (e.g., statement, emerging theme, etc.) is compared to other pieces of data and evaluated for similarities and/or differences.

Quantitative data regarding acceptability will also be collected from intervention participants through the use of weekly rating forms using Likert scales. These will be used to assess individual intervention sessions/topics. Descriptive statistics including frequencies and measures of central tendency will be calculated from these data. These acceptability scales may be administered in person or digitally.

---

### 10.3.3 ANALYSIS OF THE SECONDARY ENDPOINT(S)

Repeated measures ANOVA will be used to test the effect of the treatment on the outcomes over time. In regards to the hypotheses related to specific aim 1, outcomes including physical/emotional functioning, will be compared between treatment groups using separate repeated measures ANOVA with 5 measurement time points. Data will be presented as unstandardized beta coefficients and their respective standard errors. T-tests and chi-squares will be used to compare demographic variables between participants who complete the study and those who do not. Listwise deletion will be used when data is not missing for more than 10% of participants and there are no differences on demographic variables between completers and non-completers. If data are missing for more than 10% of participants or if there are demographic

differences between completers and non-completers, Full Information Maximum Likelihood will be used to estimate missing data.

---

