## 2.3 POTENTIAL RISKS AND BENEFITS

### 2.3.1 KNOWN POTENTIAL RISKS

There are minimal risks to study participants. However, the ACT intervention, as well as measures included in assessment for all participants, will ask participants to reflect on both physical and psychological constructs that may be related to their cancer experience. This may result in distress. In the event that distress is acute, psychosocial support will be available for all participants. It is the expectation that participants in both groups will experience some benefit from active pain management intervention. All ACT groups will be directed by a licensed clinical psychologist in order to monitor for any distress in the group. Additionally, assessments of emotional functioning and pain experience (i.e., interference and severity) will be measured at the midpoint of the intervention in order to assess for any possible iatrogenic effect. These measures are precautionary in nature as there are no known potential risks for this intervention.

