## 4 STUDY DESIGN AND ENDPOINTS

### 4.1 DESCRIPTION OF THE STUDY DESIGN

This study is a single site (University of Colorado Cancer Center), randomized control trial. It will investigate the implementation (i.e., feasibility, acceptability, and fidelity) and preliminary clinical efficacy of an ACT intervention plus TAU for chronic pain in cancer survivors compared to TAU alone. Following consent, participants will provide baseline data including demographic and clinical characteristics. Participants will be randomized to ACT plus TAU or TAU alone. Due to study design, it is not possible to blind either participants or investigators to study condition. Participants will complete assessments at baseline, 4-week intervention midpoint, 8-week intervention completion, 6-week follow-up, and 12-week follow-up.

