#### 4.2.2 SECONDARY ENDPOINTS

Changes in physical and emotional functioning in the intervention group will be compared to the control group. The primary outcomes are physical and emotional functioning as measured by the

SF-36. We hypothesize that improvements in physical and emotional functioning will occur over time in both groups, but will be greater for the intervention group at completion of the program and at six and 12-week follow-ups as compared to the control group. The SF-36 has been used in previous studies evaluating ACT and chronic pain [14, 15]. Furthermore, the use of physical and emotional functioning as primary endpoints directly aligns with the theoretical basis of acceptance-based therapies [15].

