### 10.3 DESCRIPTION OF STATISTICAL METHODS

#### 10.3.1 GENERAL APPROACH

This study will employ an effectiveness-implementation hybrid design (Type 1) [14], including a randomized controlled trial.

- Descriptive statistics: Categorical data will be presented as frequencies and percentages. Continuous variables will be presented using appropriate measures of central tendency.
- Inferential tests: Inferential tests will be one-tailed using an alpha level of .05.
- Covariates: We will compare treatment and control groups across all relevant demographic and medical variables to ensure randomization resulted in an equal distribution across groups. If differences are found among these variables, they will be included as covariates and subsequent models.
- For all dependent variables, we will check for normality by examining skew and kurtosis. For variables that violate normality, we will use nonparametric bootstrapping to estimate standard error and 95% confidence intervals. Additionally, we will also assess the data for violations of sphericity.

---

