### 10.3.10 EXPLORATORY ANALYSES

Repeated measures ANOVA will be used to test the effect of the treatment on the outcomes over time. Exploratory outcomes pain interference, pain intensity, and psychological flexibility, will be compared between treatment groups using separate repeated measures ANOVA with five measurement time points. Data will be presented as unstandardized beta coefficients and their respective standard errors. T-tests and chi-squares will be used to compare demographic variables between participants who complete the study and those who do not. Listwise deletion will be used when data is not missing for more than 10% of participants and there are no differences on demographic variables between completers and non-completers. If data are missing for more than 10% of participants or if there are demographic differences between completers and non-completers, Full Information Maximum Likelihood will be used to estimate missing data. Exploratory mediation analyses of exploratory process measures will also be conducted.

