### Aim 2:

A previous study of ACT for chronic pain management [30], using the same measures of physical and emotional functioning (e.g., the SF-36), found moderate ( $d = 0.61$ ) to large effects ( $d = 0.97$ ) at post treatment, respectively. Sample size was estimated using  $d = 0.61$ , with power at 0.80 and  $\alpha = .05$ , two-tailed. It is assumed that the correlation between pre and post-test measures will be high at .5. With these parameters and using repeated measures ANOVA to evaluate treatment difference, sample size is powered for clinical outcomes at 92 participants; with an estimated 30% attrition and conservatively including the possibility of screening failures, a maximum sample of 140 participants will be targeted for enrollment. Power was calculated using the FactorialPowerPlan Macro for SAS. See above section 10.3.2 for

missing data plan. The maximum number of participants that can be enrolled is 140, allowing for 30 % attrition and possible screening failures.

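### The efficacy analysis names no term or contrast that tests the stated hypothesis of greater improvement on ACT at week 8 and at the 6- and 12-week follow-ups, and neither arm test of a five-time-point ANOVA answers it

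*Combined protocol and SAP*

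**What the plan says.** The hypothesis in Section 4.2.2, repeated under Aim 2 in Section 2.2, is directional and tied to visits: improvement "will be greater for the intervention group at completion of the program and at six and 12-week follow-ups".

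The only efficacy analysis is in Section 10.3.3: "Repeated measures ANOVA will be used to test the effect of the treatment on the outcomes over time", with outcomes that "will be compared between treatment groups using separate repeated measures ANOVA with 5 measurement time points". Results are to be given as unstandardised coefficients with standard errors. Section 10.3.10 uses the same method, "separate repeated measures ANOVA with five measurement time points", for pain interference, pain intensity and psychological flexibility.

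Section 4.1 lists the five occasions: "Participants will complete assessments at baseline, 4-week intervention midpoint, 8-week intervention completion, 6-week follow-up, and 12-week follow-up". Baseline and week 4 are not in the hypothesis. Section 2.3.1 explains that emotional functioning and pain are "measured at the midpoint of the intervention in order to assess for any possible iatrogenic effect".

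Section 10.3.1 makes inferential tests one-tailed at 0.05 and adds: "Additionally, we will also assess the data for violations of sphericity". Section 10.4 (Aim 2) sizes the trial two-tailed at 0.05, with d = 0.61, 80% power and 92 participants: "It is assumed that the correlation between pre and post-test measures will be high at .5".

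**The concern.** A two-arm ANOVA with five occasions gives two tests that involve arm. The arm main effect averages the arm difference over all five occasions, including baseline, where randomisation makes the expected difference zero, and week 4, about which the hypothesis is silent. The arm-by-time F has 4 numerator degrees of freedom and asks only whether the arm difference varies across occasions. It does not say when, or in whose favour. Nor can a 4-df F be run one-tailed, as Section 10.3.1 requires.

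The plan names neither test as decisive. It gives no follow-up procedure after a significant F and no rule for what counts as success. A significant effect over time could therefore be reported when nothing happened at the three hypothesised visits, or the deciding coefficient could be picked once the data are known.

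**Working it through.** **Inputs.** Section 10.4: d = 0.61, correlation 0.5, two-sided 0.05, 92 participants. Section 10.5.1: 1:1 allocation, hence n = 46 per arm. Assumed here, because the plan does not say: SD 1 at every occasion and equal correlation between all pairs of occasions (compound symmetry). Effect patterns are ACT minus TAU at baseline, week 4, week 8, 6-week and 12-week follow-up.

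**The plan's own figure.** A two-sample t-test at d = 0.61 needs 44 per arm (88). A pre-post change score gives the same number, since its variance is 2(1 − 0.5) = 1. At 46 per arm the power is 82.5%. The stated 92 is not reproduced exactly, but it is close and on the safe side. The macro settings are not given, and nothing below depends on them.

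**Arm-by-time F.** The degrees of freedom are 4 and 4 × 90 = 360. The noncentrality is λ = (n/2) Σ(δt − mean δ)² / (1 − r).

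- Sustained benefit (0, .61, .61, .61, .61): mean .488; sum of squares .488² + 4 × .122² = .298; λ = 23 × .298 / .5 = 13.7; power .85.
- Week 4 only (0, .61, 0, 0, 0): mean .122; sum of squares .488² + 4 × .122² = .298; λ = 13.7; power .85, identical to the line above.
- ACT worse at all three visits (0, 0, −.61, −.61, −.61): mean −.366; sum of squares 2 × .366² + 3 × .244² = .447; λ = 20.5; power .97.
- Mixed pattern ending in harm (0, .3, 0, −.3, −.3): sum of squares .252; λ = 11.6; power .78.

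**Arm main effect.** The SD of a participant's five-occasion mean is √[(1 + 4 × .5)/5] = √.6 = .775.

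**Contrast of the three hypothesised visits.** Take the mean of week 8, 6-week and 12-week follow-up, minus baseline. Its variance is 1 + (1 + 2 × .5)/3 − 2 × .5 = .667, SD .816. For a sustained .61 the standardised effect is .61/.816 = .747, the noncentrality .747 × √23 = 3.58 on 90 df, and the power .94. For a fading effect (.61, .45, .30) the mean is .453, the standardised effect .555 and the power .75.

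| Pattern at the three visits | Week-4 effect | Main effect | Arm-by-time F | Contrast |
|---|---|---|---|---|
| .61 sustained | 0 | .61 | .97 | .94 |
| .61 sustained | .305 | .74 | .85 | .94 |
| .61 sustained | .61 | .85 | .85 | .94 |
| .61, .45, .30 | .305 | .53 | .68 | .75 |
| none | .61 | .12 | .85 | .05 |

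The main effect in the last row is .122/.775 = .157 in SD units. The contrast there rejects at its nominal 5%.

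**Sensitivity of the week-4-only result for the F.** It is about 70% at r = .3 (λ = 9.8) and 98% at r = .7 (λ = 22.8). If correlation decays with time (.5 at 8 weeks) and a sphericity correction is applied, simulation gives 81%, against 74% for a sustained benefit. At 25 per arm, the minimum enrolment of 50, it is 56%; for harm at all three visits it is 76%. The contrast's power for a sustained .61 is .85 at r = .3, above .99 at r = .7 and .81 under the decaying correlation.

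**Visits taken singly.** Each change from baseline has 82.5% power. Significance at all three has about 65%.

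**The case against.** The strongest reply is that Section 10.3.3 never says an F-test decides anything. It promises coefficients, which carry signs, and one-tailed testing makes more sense for coefficients than for a 4-df F. An analyst who reads the signs would not report harm as benefit. This stands: a reader might infer that the plan would call a reversed effect a success, and the documents do not support that. What remains is that no coefficient is named and no test is attached to one.

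A reader might also infer that the plan inflates type I error. An uncorrected F under decaying correlation does reject in about 7% of null trials by simulation. But that figure needs complete data and a sphericity violation that is found and then ignored. Section 10.3.1 says sphericity will be assessed, a standard correction brings the rate back to about 5%, and Section 10.3.3 moves to full information maximum likelihood once more than 10% of participants have missing data, with 30% attrition expected. The gap is only that no action follows the sphericity check.

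A third inference, that the 92 was computed for a pre-post comparison, is plausible from the single correlation but is not shown. Section 10.4 says repeated measures ANOVA was used.

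Low power is not the main issue: for a sustained 0.61 the arm-by-time F exceeds 80% in every case tabulated.

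Finally, an averaged contrast is not the hypothesis visit by visit either. An effect of 1.2 at week 8 only gives .4/.816 = .49 and significance in 64% of trials; the pattern .9, .6, −.1 gives .467/.816 = .57 and 77%. This also stands, and the remedy must allow for it.

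**Conclusion.** The point holds as a mismatch between hypothesis and analysis. Sections 10.3.3 and 10.3.10 leave unnamed the quantity that tests the visit-specific hypothesis, and neither arm test the ANOVA supplies would serve. The arm-by-time F responds equally, at 85%, to a sustained benefit and to an effect at week 4 alone, and at 97% to harm of the same size at all three visits. The power of the main effect moves from .61 to .85 with a week-4 effect that the hypothesis does not mention.

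These figures rest on 46 per arm, equal SDs and compound symmetry at 0.5. The sensitivity results change the percentages but not the finding that the F cannot separate the patterns. Neither inflated type I error nor a pre-post basis for the sample size is part of this conclusion.

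Efficacy is the secondary and preliminary objective, so the feasibility, acceptability and fidelity conclusions are untouched. The change should be made, but the trial's primary purpose does not hang on it.

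**What to change.** In Sections 10.3.3 and 10.3.10, replace the omnibus ANOVA test with ACT-minus-TAU contrasts in change from baseline, from a likelihood-based mixed model with five time points and unstructured covariance. This fits the missing-data method already planned and needs no sphericity assumption.

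- Name one deciding contrast per outcome. The mean of week 8, 6-week and 12-week follow-up minus baseline is one option; each visit, or all three together, are others, with the powers shown above.
- Always report the three single-visit differences with confidence intervals, and claim benefit at a visit only from that visit's own difference.
- Treat week 4 as descriptive in the efficacy analysis.
- Make the sidedness agree between Sections 10.3.1 and 10.4, and restate the power in Section 10.4 for the chosen contrast.

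The cost is wording: no new data, visits or participants. The averaged contrast can be significant when the effect sits at one visit, and it can also dilute such an effect, so the single-visit results must accompany it. The trial is open-label, was under way when this version was dated (March 2021; its in-person phase began in January 2019), and Section 10.3.6 has investigators monitoring data throughout. The change should therefore be a dated amendment that gives its reasons and states what outcome data had been seen.

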#### **10.3.4 ADHERENCE AND RETENTION ANALYSES**

Feasibility is a key outcome of the implementation aim for this study. Participant eligibility, enrollment, and completion of study intervention and assessments will be tracked through standardized databases (e.g., screening and enrollment). We will also track completion of assessment measures through REDCap. Percentages for each relevant domain will be calculated. Individuals who do not complete assessment time points as prescribed will be contacted by research staff in order to minimize missing data. Participants who choose to withdraw from the study will be contacted to confirm their decision and will be asked why they are choosing to discontinue participations (e.g., time, medical issues, does not feel intervention is helpful). This information will be used to inform future studies and relevant grant applications.

---

#### **10.3.5 BASELINE DESCRIPTIVE STATISTICS**

Relevant demographic constructs (i.e., age, race/ethnicity), as well as baseline assessments of primary and exploratory measures (e.g., physical and emotional functioning, pain severity and intensity, and measures of psychological flexibility), will be compared using two sample t-tests and chi-square analyses.

---

#### **10.3.6 PLANNED INTERIM ANALYSES**

Given that the secondary aim is feasibility and the exploratory aim is to test possible process measures, study investigators will monitor data throughout the project.

---

#### **10.3.7 ADDITIONAL SUB-GROUP ANALYSES**

Subgroup analyses comparing outcomes for participants who received the intervention in-person versus those who received the intervention remotely will be conducted.

---

#### **10.3.8 MULTIPLE COMPARISON/MULTIPLICITY**

Multiple comparisons are not an area of concern for our study design.

---

#### **10.3.9 TABULATION OF INDIVIDUAL RESPONSE DATA**

Individual data will be entered into REDCap using each patient's unique study identification number and will be listed by measure and time point.

### 10.3.10 EXPLORATORY ANALYSES

Repeated measures ANOVA will be used to test the effect of the treatment on the outcomes over time. Exploratory outcomes pain interference, pain intensity, and psychological flexibility, will be compared between treatment groups using separate repeated measures ANOVA with five measurement time points. Data will be presented as unstandardized beta coefficients and their respective standard errors. T-tests and chi-squares will be used to compare demographic variables between participants who complete the study and those who do not. Listwise deletion will be used when data is not missing for more than 10% of participants and there are no differences on demographic variables between completers and non-completers. If data are missing for more than 10% of participants or if there are demographic differences between completers and non-completers, Full Information Maximum Likelihood will be used to estimate missing data. Exploratory mediation analyses of exploratory process measures will also be conducted.

## 10.4 SAMPLE SIZE

### Aim 1:

Given that the primary aim of this study is the feasibility of implementation, a minimum of  $n = 50$  will be set for recruitment. This is generally discussed as a moderate sample size in feasibility pilot studies in clinical research [25-27].

In qualitative research, it is generally accepted that data collection continues until “saturation” has been met [28]. Saturation occurs once a researcher has collected enough case data that data provided by additional cases does not provide new information or themes. It has been suggested, for studies that utilize individualized interviews to develop and understand nuances of theory, that between 12-30 participants are typically needed to reach saturation [28, 29]. This will be the targeted sample size range for the qualitative interviews.

### Aim 2:

A previous study of ACT for chronic pain management [30], using the same measures of physical and emotional functioning (e.g., the SF-36), found moderate ( $d = 0.61$ ) to large effects ( $d = 0.97$ ) at post treatment, respectively. Sample size was estimated using  $d = 0.61$ , with power at 0.80 and  $\alpha = .05$ , two-tailed. It is assumed that the correlation between pre and post-test measures will be high at .5. With these parameters and using repeated measures ANOVA to evaluate treatment difference, sample size is powered for clinical outcomes at 92 participants; with an estimated 30% attrition and conservatively including the possibility of screening failures, a maximum sample of 140 participants will be targeted for enrollment. Power was calculated using the FactorialPowerPlan Macro for SAS. See above section 10.3.2 for

missing data plan. The maximum number of participants that can be enrolled is 140, allowing for 30 % attrition and possible screening failures.

## 10.5 MEASURES TO MINIMIZE BIAS

### 10.5.1 ENROLLMENT/ RANDOMIZATION/ MASKING PROCEDURES

There is no blinding in this study. Enrolled participants will be randomly assigned at a 1:1 ratio to receive eight weekly group-based ACT sessions plus TAU or TAU alone. The REDCap randomization tool will be used to facilitate randomization.

## 11 SOURCE DOCUMENTS AND ACCESS TO SOURCE DATA/DOCUMENTS

Appropriate research records will be maintained as necessary and in compliance with regulatory and institutional requirements for the protection of confidentiality of participants.

It is expected that the majority of data collection will occur via REDCap, so it is likely any creation of source documents will be minimal.

This study may collect source data from hospital records, fidelity checklists, paper versions of questionnaires, recorded audio tapes and transcriptions of interviews. These will be kept in de-identified labeled binders/folders in a locked cabinet in a locked office.

## 12 QUALITY ASSURANCE AND QUALITY CONTROL

Quality Control (QC) procedures will be implemented beginning with the data entry system and data QC checks that will be run on the database will be generated. Any missing data or data anomalies will be communicated to the site(s) for clarification/ resolution.

Following written SOPs, the study monitor will verify that the clinical trial is conducted and data are generated, documented (recorded), and reported in compliance with the protocol, GCP, and the applicable regulatory requirements (e.g., Good Laboratory Practices (GLP), Good Manufacturing Practices (GMP)).

The investigational site will provide direct access to all trial-related sites, source data/ documents, and reports for the purpose of monitoring and auditing by the DSMC audit team, and inspection by local and regulatory authorities.

